12.6 Efficacy

12.6.1 Primary Efficacy Analysis

The following primary efficacy analyses will be carried out using the ITT population with multiple imputation as described in Section 7.1. The primary efficacy analysis will test the null hypothesis that the response probability on the primary efficacy endpoint is less than or equal to 50%. The alternative hypothesis for the primary analysis is that patients receiving the treatment have above 50% probability to achieve clinical improvement, as follows:

$$H_0: \pi_{Renova} \leq \pi_{PG}$$

$$H_1: \Pi_{Renova} > \Pi_{PG}$$

where π_{Renova} is the proportion of subjects meeting the pre-defined success criterion with RENOVA therapy (\geq 50% improvement in average number of urge related incontinence episodes, measured by a 7-day Patient Voiding Diary at 6 months post system activation), and π_{PG} is the prespecified performance goal (PG) of 50%.

Although sample size was conservatively calculated under an Exact Binomial test, the hypothesis will be tested by performing the logistic regression on each imputed dataset as described in Section 7.1. Then SAS PROC MIANALYZE procedure will be used to calculate the combined confidence interval and the corresponding p-value.

We will declare success on this endpoint if the lower limit of the confidence interval is above 50%.

Document ID	Revision / Date	Page
G02-CLP-0009	Rev. 06 / 18 May 2022	21 of 26

12.6.2 Secondary Efficacy Analysis

The following secondary efficacy analyses will be carried out using the ITT, PP and OR1 populations:

- The analysis carried out as the primary efficacy analysis will be repeated on the PP and OR1 populations.
- The secondary endpoints will be presented according to the following performance goals stated for each:
 - Proportion of subjects with ≥10 points (MID) improvement compared to baseline in HRQL (based on OAB-q) at 6 months post system activation with PG of 50%.
 - Proportion of responders at 12 months post system activation as demonstrated by ≥50% improvement in either average number of urgency related incontinence episodes or average number of large (severe) urgency related incontinence episodes, as measured by 7-day Patient Voiding Diary, with PG of 50%.
 - Proportion of responders at 6 months post system activation as demonstrated by ≥50% improvement in the average number of moderate-severe urgency episodes PPIUS degree 3,4 or <8 voids/day with PG of 45%.

Hypothesis testing for the secondary endpoints will be performed in the same manner described for the primary endpoint with respect to multiple imputation. Success on each of the secondary endpoints will be declared if the lower bound of this confidence interval is above the stated performance goal.

12.6.2.1 Multiple Comparisons for Secondary Analyses

The secondary hypotheses will be tested only if the null primary is rejected.

The secondary endpoints will be tested using Hochberg step-up procedure to control the overall type I error rate.

The calculation of each comparison to performance goal will be performed separately rather than simultaneously, as done in the Hochberg procedure. In addition, each hypothesis will be tested with two-sided (unadjusted) Alpha = 0.05.

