10.3.2 Secondary Endpoints

Bluewind will test three secondary endpoints. In order to control type I error of the family of secondary objectives at 5%, secondary objective hypothesis testing will only occur upon rejection of the primary objective null hypothesis.

- Proportion of subjects with ≥10 points (MID) improvement in HRQL (based on OAB-q) at 6 months post system activation
- Proportion of responders at 12 months post system activation as demonstrated by ≥50% improvement in either average number of urgency related incontinence episodes or average number of severe/large urgency related incontinence episodes, as measured by 7-day Patient Voiding Diary.

Number	Revision / Date	Page
G02-CLP-0002_US	Rev. 08 / 27 July 2021	30 of 75

 Proportion of responders at 6 months post system activation as demonstrated by ≥50% improvement in the average number of moderate-severe urgency episodes PPIUS degree 3,4 or <8 voids/day

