12.1 Monitoring Procedures and Responsibilities

Monitoring visits will be conducted at the start, during, and at the closure of the clinical study in accordance with study Monitoring Plan and in compliance with recognized Good Clinical Practices, FDA's IDE guidance document, as outlined in 21CFR§812.43(d) and 21CFR§812.46 and ISO 14155:2011 and per company's (or company designee) standard operating procedure. The Monitoring Plan will be included in a separate document and maintained by the study manager or designee. The Monitoring Plan will include detailed descriptions for each type of visit to be made during the study, including pre-study visits, site initiation visits, interim monitoring visits and close-out visits.

It is the responsibility of the study sponsor to ensure that proper monitoring of the investigation is conducted. This includes ensuring subject and investigator compliance to the protocol and study agreements, adherence to regulations, and accuracy of study data.

The clinical monitor, as a representative of the sponsor, has the obligation to follow the study closely. In doing so, the monitor will visit the principal investigator and/or sub-investigator(s) and study center at periodic intervals, in addition to maintaining necessary telephone and letter contact. The monitor will maintain current personal knowledge of the study through observation, review of study records and source documentation, and discussion of the conduct of the study with the principal investigator and staff.

All aspects of the study will be carefully monitored for compliance with applicable government regulations, with respect to current ISO 14155:2011 and Declaration of Helsinki regulations, and current SOPs.

The following factors will be taken into account when determining the frequency of monitoring visits at each center: implantation rate, total number of subjects enrolled, study phase (e.g., screening, treatment, long-term follow-up), center compliance, and monitoring findings from previous visits. The frequency of interim monitoring visits will be documented in the monitoring plan and approval from sponsor prior to each interim monitoring visit is required.

13. Statistical Considerations

This section describes the statistical methods that will be applied to the study's main endpoints. A detailed statistical analysis plan (SAP) will be written and finalized prior to trial initiation.

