7.1 ITT population

Treatment of missing values:

- Subjects missing data "not in random" will be imputed as "failure" on dichotomous endpoints.
- "Failures" (not MAR) include:
 - Subject leaves the study due to related AE
 - Device explant
 - o Lack of effect that results in significant increase of UUI medication
 - Need for other 3rd line therapies for the management of UUI

Document ID	Revision / Date	Page
G02-CLP-0009	Rev. 06 / 18 May 2022	11 of 26

- Baseline values will not be imputed
- Missing values in ITT not due to "failure" will be imputed using multiple imputation (MI).

Multiple imputation will be applied to the primary and three secondary endpoints. The 'additional endpoint' analyses will not use multiple imputation. The imputation procedure will be performed on the continuous outcomes (e.g. number of incontinence episodes). Based on the imputed continuous outcome, the response will be defined accordingly for each endpoint.

The hypotheses will be tested by performing the logistic regression on each imputed dataset. Then SAS PROC MIANALYZE procedure will be used to calculate the combined confidence interval and the corresponding p-value. The evaluation on each endpoint will be successful if the lower limit of the confidence interval is above 50%. In addition, the primary analysis will present the observed frequency of responders and descriptive statistics of response rates over all imputed datasets.

Fifty (50) imputed datasets will be created (the seed is set to 123456).

The imputation will be done using covariates: Age, BMI, average number of urgency leaks, average number of urgent voids, HRQL score and OAB duration at baseline. This list might be reduced if the model fails to converge.

Because MI assumes missing at random (MAR), sensitivity analyses (i.e. tipping point) described below, will be conducted to test the effects of other patterns of missingness.

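### SAP 12.6.2.1 names Hochberg for the three secondary endpoints and also unadjusted testing at two-sided 0.05, without saying which decides success

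*SAP*

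**What the plan says.** SAP 12.6.2.1 tests the secondary hypotheses only after the primary null is rejected. It continues: "The secondary endpoints will be tested using Hochberg step-up procedure to control the overall type I error rate". Next comes "The calculation of each comparison to performance goal will be performed separately rather than simultaneously, as done in the Hochberg procedure", and then "In addition, each hypothesis will be tested with two-sided (unadjusted) Alpha = 0.05". No sentence ranks these statements.

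The operative success rules stand elsewhere:

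- SAP 12.6.2: "Success on each of the secondary endpoints will be declared if the lower bound of this confidence interval is above the stated performance goal". The goals there are 50% for the HRQL endpoint, 50% for the 12-month leak endpoint, and for the urgency (PPIUS) endpoint "moderate-severe urgency episodes PPIUS degree 3,4 or <8 voids/day with PG of 45" percent.
- SAP 7.1, whose imputation rules cover the primary and all three secondaries: "The evaluation on each endpoint will be successful if the lower limit of the confidence interval is above 50" percent.

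Protocol 10.3.2 relies on first rejecting the primary null: "In order to control type I error of the family of secondary objectives at 5%, secondary objective hypothesis testing will only occur upon rejection". It does not say whether its 5% is one- or two-sided. Protocol section 13 leaves the detail to the SAP: "A detailed statistical analysis plan (SAP) will be written and finalized prior to trial initiation".

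**The concern.** Hochberg and endpoint-by-endpoint testing at an unadjusted level are different decision rules. The first looks at the three p-values together and tightens the threshold once the largest p-value fails. The second never tightens it. A plan that names both, and whose success sentences follow the second, lets the same data be reported as a success or not, depending on the sentence cited.

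The condition in Protocol 10.3.2 does not settle this. Requiring the primary to succeed first protects the secondaries only while the primary null is true. Once the primary is rejected, it gives no protection among three further tests.

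At stake is the error control that both documents claim for the secondary family. One member, the PPIUS endpoint, also drives the total of 150 subjects.

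**Working it through.** **1. The plan's own figure.** SAP section 9 sizes the PPIUS endpoint with goal 45%, assumed rate 61%, one-sided 0.025 and power of at least 85%. With an exact binomial test, the smallest n that works is 89. The critical count is 50, with P(X ≥ 50 | 0.45) = 0.0223 and P(X ≥ 50 | 0.61) = 0.851. Then 89/0.85 ≈ 105 and 105/0.70 = 150. The stated figures reproduce, and they rest on the full unadjusted one-sided 0.025.

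**2. The two rules, one-sided in the favourable direction.**

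- Unadjusted: endpoint i succeeds if its p ≤ 0.025.
- Hochberg: if the largest p ≤ 0.025, all three succeed. Otherwise, if the second-largest p ≤ 0.0125, the two smaller succeed. Otherwise, if the smallest p ≤ 0.025/3 = 0.00833, that one succeeds.

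If all three p-values are at most 0.025, both rules give three successes. They can differ only when one or two clear.

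**3. Chance of at least one false success, given that the secondaries are tested.** Under independence the unadjusted rule gives 1 − 0.975³ = 0.0731 with three true nulls and 1 − 0.975² = 0.0494 with two. For other correlations (assumed, because the documents give none), equicorrelated normal statistics were simulated:

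| Correlation | 0 | 0.3 | 0.5 | 0.7 | 0.8 | 0.9 |
|---|---|---|---|---|---|---|
| Three true nulls, unadjusted | 7.3% | 6.8% | 6.3% | 5.4% | 4.9% | 4.2% |
| Three true nulls, Hochberg | 2.5% | 2.4% | 2.3% | 2.0% | 1.9% | 1.7% |
| Two true nulls, unadjusted | 4.9% | 4.8% | 4.5% | 4.2% | 3.9% | 3.5% |
| Two true nulls, Hochberg | 2.5% | 2.5% | 2.4% | 2.3% | 2.2% | 2.1% |

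The two-null rows take the third endpoint as certain to pass. With one true null and the other two endpoints certain to pass, both rules give 2.5%.

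**4. How often the decisions differ when all three endpoints truly beat their goals.** Power per endpoint is assumed; ranges are over correlations 0 to 0.9.

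| Power of each endpoint | Trials with different decisions |
|---|---|
| 80% | 9.6% to 12.7% |
| 90% | 3.3% to about 7% |
| 95% | 1.1% to about 4% |

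The rules never differed when all three endpoints cleared.

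**5. A concrete case: PPIUS, n = 89, goal 45%.** The exact test is the one used for sizing. SAP 12.6 analyses by logistic regression; with no missing data this is a Wald test on the logit, z = [ln(x/(89−x)) − ln(0.45/0.55)] / √(1/x + 1/(89−x)).

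| Responders x | Exact p | Logit-Wald p |
|---|---|---|
| 50 | 0.0223 | 0.0178 |
| 51 | 0.0132 | 0.0105 |
| 52 | 0.0075 | 0.0059 |

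- 50 responders: a success unadjusted, but not under Hochberg if either other endpoint misses. This holds for both tests.
- 51 responders: the same under the exact test. Under the Wald test, 51 still passes Hochberg if exactly one other endpoint misses and the remaining one has p ≤ 0.0125. It fails if both others miss.
- 52 or more: a success under both rules and both tests.

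**6. Power of PPIUS at a reduced step.** At n = 89 the exact critical count rises from 50 to 52 at either 0.0125 or 0.00833, and power falls from 85.1% to 72.9%. By the Wald test, power is 79.6% at 0.0125 and 72.9% at 0.00833.

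**The case against.** The strongest reply is that the intended reading is clear. The one subsection devoted to multiple comparisons says Hochberg is used to control error. Hochberg takes separately computed raw p-values and compares the largest with the full alpha, so the remarks on separate calculation and unadjusted 0.05 may only describe its inputs and first step. Section 12.6.2.1 also sits under 12.6.2 and may qualify the success sentence there. This reading is reasonable, but it is not written down. The sentence about 0.05 is introduced as an addition to Hochberg, and neither success sentence mentions ordering or reduced levels.

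Second, 7.3% is a remote case. It needs the primary to succeed while all three secondary nulls are true. The 12-month endpoint accepts a reduction in either all leaks or large leaks, against the same 50% goal as the primary, so its null would mean that the effect had faded. If PPIUS truly reaches the 61% assumed in SAP section 9, at most two nulls are true and the unadjusted rule stays at or below 4.9%. That stands: a one-sided 5% target is exceeded only with three true nulls and correlation below about 0.8. A one-sided 2.5% target, however, is already exceeded with two true nulls.

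Third, the 50% printed in SAP 7.1 is a performance-goal slip rather than a multiplicity error, and 12.6.2 gives the right value. That is fair, but the sentence is one of the two that define success and needs the same edit.

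**Conclusion.** The concern holds. The SAP contains two decision rules for the secondary family, its success sentences follow the one without step-up, and control of the family is therefore not assured when only one or two endpoints clear. It is not shown to be lost, because control is kept if Hochberg is what decides.

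If the unadjusted sentences decide, the one-sided chance of any false secondary success is 4.2% to 7.3% with three true nulls and 3.5% to 4.9% with two, against at most 2.5% under Hochberg. These figures rest on assumed equal correlations between 0 and 0.9 and do not model correlation with the primary. The disagreement rates also rest on assumed power, since the documents give none for the HRQL and 12-month endpoints. The primary analysis is untouched. This should be fixed before database lock.

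**What to change.** 1. In SAP 12.6.2 and 12.6.2.1, state that secondary success is decided only by Hochberg on the three separately computed p-values in the ITT set with multiple imputation. Give the steps: one-sided 0.025, 0.0125 and 0.00833, equivalently two-sided 0.05, 0.025 and 0.0167. State that unadjusted 95% intervals and the PP and OR1 results are supportive.
2. In SAP 7.1, refer the success sentence to that rule and to each endpoint's own performance goal, which is 45% for PPIUS.
3. In Protocol 10.3.2, name the same procedure and state the sidedness of the 5%.

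Two optional additions would help. SAP 1.1 plans a full analysis and submission at 6 months, with the 12-month endpoint evaluated later, so the step-up cannot in general be completed at 6 months. The SAP could say which secondary claims may be made then; treating the outstanding p-value as 1 is one valid convention. SAP section 9 could note that the 85% power for PPIUS applies at unadjusted one-sided 0.025 and is lower at a reduced step.

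The cost is SAP and protocol wording, with no new data or patients. The downside is that a borderline secondary claim may be lost, or delayed until the 12-month result.

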12.6.3 Additional Efficacy Analysis

The additional efficacy endpoints will be assessed descriptively on the ITT, PP and OR1 populations. Descriptive statistics will be provided for diary parameters collected within the Axiom data management report and will include the following by visit for each diary period available:

- Patient Global Impression of Improvement (PGI-I) score
- Treatment Benefit, Satisfaction, and Willingness to Continue (BSW)
- Improvement in OABq (HRQL (and its subscales) and symptoms severity)
- Changes in the following OAB symptoms as measured by voiding diary 6 and 12-months post system activation compared to baseline:
- Reduction in the average number of severe/large urgency related incontinence episodes
- Reduction in the number of micturition episodes.
- Reduction in the number of nocturia episodes.

Document ID	Revision / Date	Page
G02-CLP-0009	Rev. 06 / 18 May 2022	22 of 26

- Reduction in the number of urgency related incontinence episodes.
- Reduction in degree of urgency prior to void on Patient Perception of Intensity of Urgency Scale (PPIUS) from 0-4.
- Reduction in severity of incontinence episodes (amount leaked).
- Proportion of dry subjects following treatment with the RENOVA iStim System as measured by 3
 consecutive days of a patient voiding diary.
- Assessment of fecal incontinence symptoms in patients suffering from mixed fecal and urine incontinence.
- Device usage
- Patient compliance with treatment through 6-months
- Descriptive statistics of percent compliance with treatment will be presented by center and visit.

12.7 Sensitivity Analysis

To evaluate robustness of the study's primary outcome, an alternative imputation methodology will be examined to assess sensitivity. The primary analysis will utilize multiple imputation.

Tipping Point Imputation

Different proportion of subjects with missing data will be imputed best or worst imputation progressively until the tipping point is reached; i.e. missing cases will be progressively imputed "failure" until the primary analysis is no longer significant (the tipping point).

12.8 Covariate, Subgroup, and 'Poolability' Analyses

Covariate analyses will be done by comparing the primary endpoint by the levels of the covariate at baseline, where continuous variables will be coded into two levels by median split. Analyses will be done by logistic regression. Covariates will include, but are not limited to:

- Age
- BMI
- OAB duration at baseline
- US vs. Outside of US (OUS)
- Race and ethnicity
- Baseline average urgency leaks/day
- Baseline average voids/day
- Smoking history (Past/Current/Never)
- Concomitant OAB medication at time of screening
- Ratio between average stress related leaks and average urgency related leaks at baseline.

For each of the listed above covariates descriptive statistics of the primary endpoint by covariate levels will be

Document ID	Revision / Date	Page
G02-CLP-0009	Rev. 06 / 18 May 2022	23 of 26

presented. Continuous covariates will be divided into quartiles for this presentation. Additionally, formal subgroup analyses will be conducted to assess the effects on the primary endpoint of antidepressant medications and OAB medication, and also to assess the potential impact of COVID-19 on the study outcomes.

The analyses for antidepressant medications and OAB medications will be structurally similar. The first level of the analyses for each medication type will compare treatment effect (success rates) among those taking and not taking the respective medication at baseline. This will be performed as a logistic regression model, with baseline status as an indicator variable. If there is no difference in outcome, the second level of the analysis will be a logistic regression analysis on all subjects, with an indicator variable for changes in medication (lower, same or higher total dosage). If there is a differential effect concerning baseline status, the second level analysis will be comprised of two analyses; one only consisting of the subjects on the respective medication at baseline, with an indicator for any subsequent changes, and this will be repeated for the complementary subgroup of those subjects not on the respective medication at baseline. For each level of analysis, the success rate for each level of the subgroup will be reported for completeness. It should be noted that changes in usage of antidepressants and OAB medications will need to be defined and filtered from the concomitant medications form in exploratory fashion.

Any subjects enrolled prior to the COVID-19 outbreak may be subject to telephone follow-ups instead of onsite follow-up visits for a period of time. Interactions with affected subjects, then, would be different than for those who are routinely followed in the clinic, and only a subset of data will be able to be collected. A covariate adjusted logistic regression model, as described above, will be fit to assess the potential impact of COVID-19 on study outcomes, with an indicator variable indicating subjects enrolled prior to, and after, stay- at-home policies were enacted.

Finally, a test of homogeneity of effect across investigational center will be conducted. Descriptive statistics (e.g. success rate) will be reported for every participating center. Any center enrolling fewer than five subjects will be excluded from the formal test of homogeneity. To acknowledge that this test of homogeneity is fundamentally underpowered, a significance level of 0.15 will be used to determine whether a potential differential effect across centers exists and to trigger additional, exploratory analysis to better understand the nature of the difference.

13 Long-Term Follow-Up

Upon completion of the 12-month follow-up visits, patients will enter a long-term follow-up phase. Formal study visits will occur at 24 and 36 months. Less comprehensive visits conducted via telephone will be conducted at months 18 and 30. The telephone visits will assess adverse events and subject diary data.

Document ID	Revision / Date	Page
G02-CLP-0009	Rev. 06 / 18 May 2022	24 of 26

All primary, secondary and additional efficacy measures will be summarized using appropriate descriptive statistics - mean, median, standard deviation and 95% confidence intervals for continuous measures and frequency distributions for categorical or binary data. Adverse events, and treatment regimen data will be summarized.

14 Data Listings

Data listings will be provided for all data available from the CRF.

15 Computer Software

All statistical analyses will be carried out using SAS® Version 9.4 or higher under Windows® 2016 Terminal.

Document ID	Revision / Date	Page
G02-CLP-0009	Rev. 06 / 18 May 2022	25 of 26

16 Appendix 1: Rules for Correction of Discrepancies in Paper Diaries

Since querying of paper diaries is not possible at the time of completion and not feasible in an accurate manner afterwards, no query management process is used for the paper diaries. In its place the following set of automatic rules will be applied to correct discrepancies in the paper diaries. The rules will be determined before database lock.

17 Appendix 2: Rules for Diary Calculations

Diary calculation will be added before database lock.

Document ID	Revision / Date	Page
G02-CLP-0009	Rev. 06 / 18 May 2022	26 of 26
